## **3.2 Exclusion Criteria**

The subject may be excluded or withdrawn from the study if any of the following apply:

**3.2.1** Patients receiving WBRT without the use of a CT or MRI-based planning simulation.

**3.2.2** Patients receiving WBRT with the use of intensity-modulated radiation therapy.

**3.2.3** Patient receiving WBRT as elective treatment of potentially subclinical intracranial disease (e.g., WBRT for prophylactic cranial irradiation of small cell lung cancer).

[figure not shown]
**3.2.4** Physically unable to communicate by paper or phone to complete the study survey.

**3.2.5** Prisoners.

**3.2.6** Pregnant women.

## 4.0 STUDY PLAN

### 4.1 Schema

Note: Due to the expedited nature of many whole brain radiation treatment plans, we anticipate identifying many subjects after treatment has already begun. Because of this, we will offer these individuals enrollment on an observational arm of this study. Additionally, if participants do not wish to participate in the interventional arm of this study, they will be approached for the observational arm. See Section 4.3 for more details.

### 4.2 Duration of Study

The anticipated accrual period is around 3-5 years.

### **4.3 Study Details**

This is primarily a two-arm, single-blind, randomized study of parotid sparing WBRT, with a third observational arm of patients who were identified after radiation had already started or who refused randomization but were willing to be followed for quality of life assessment. The primary purpose of this study is to compare the proportion of patients experiencing significant xerostomia in patients randomized to parotid sparing vs. standard WBRT. Patients receiving WBRT often receive treatment in urgent situations, making pre-treatment randomization logistically challenging. Therefore, the observational arm serves to increase the number of eligible patients and allows for comparison of xerostomia in all patients receiving parotid sparing vs. standard WBRT, but who were unable to be approached in time for randomization. Patients enrolling on the randomization arms will be consented and enrolled prior to treatment. Patients enrolling on the observational arm may enroll up to 5 days after initiation of treatment. Post-treatment surveys will be collected up to 6 months post-RT. We therefore anticipate that patients' active participation will last approximately 6 months. Chart abstraction will take place for up to 1 year post-RT for assessment of secondary endpoint #1: freedom from marginal relapse.

#### **4.3.1 Screening for Eligibility and Registration Details**

Patients identified as qualifying for the trial will be divided into those who were identified prior to radiation start vs. those identified after radiation start. Patients interested in participating will complete an anonymous screening baseline xerostomia questionnaire identical to the primary study assessment (see Section 4.3.9, below). Patients scoring  $\geq 40$  pts on the screening xerostomia questionnaire are ineligible. Patients scoring  $< 40 / 80$  will be eligible and offered enrollment on the study. Questionnaires completed by patients who are found to be ineligible or who decline to enroll on the study will be destroyed. Questionnaires completed by patients who consent to the trial will be assigned patient information (de-anonymized) and serve as their baseline quality of life data.

Patients identified prior to radiation start will be offered enrollment into the randomization arms (Consent form 1, arms A and B), with the observation arm (Consent form 2, arm C) offered to those who refuse randomization. Patients identified after radiation has already started, but within 5 days of the first day of radiation, will be offered enrollment into the observational arm (Consent form 2, arm C).

#### **4.3.2 Randomization Details**

Patients who agree to be randomized will be assigned to one of the following treatment groups using block randomization. A randomization list will be designed by the statistician. Patients will be randomized after informed consent is obtained, and before treatment begins. A list of randomized assignments will be provided to each site prior to enrollment of participants to facilitate ease of trial administration. This is done because of the often urgent nature of whole

brain cases and the necessity of clinicians knowing the randomized assignment before treatment planning.

Arm A: Standard WBRT (Control)

Arm B: Parotid sparing WBRT (Intervention)

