#### 4.3.7 Treatment Planning and Delivery – Arm C: Observational arm (WBRT protocol not specified)

Patients who decline randomization but consent to the observational arm will receive WBRT without the use of the above treatment planning guidelines. WBRT will be delivered using standard or parotid sparing fields, per treating physician preference. Patients may also enroll on this arm after initiation of WBRT, as long as the baseline questionnaire is completed within 5 days of initiation of treatment. These patients will complete the protocol-specified study assessments at the same time points as randomized patients.

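### Sites receive the list of randomized assignments before enrollment, and nothing in the plan conceals the next assignment from recruiting or treating staff

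*Combined protocol and SAP*

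**What the plan says.** Section 4.3.2 states that patients will be "assigned to one of the following treatment groups using block randomization", from a list designed by the statistician. On timing it says: "Patients will be randomized after informed consent is obtained, and before treatment begins". It then adds: "A list of randomized assignments will be provided to each site prior to enrollment of participants to facilitate ease of trial administration". The reason given is the urgency of whole brain cases and "the necessity of clinicians knowing the randomized assignment before treatment planning". Block size, fixed or varying blocks, and stratification are not stated.

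Other sections bear on the point:

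- **Section 4.3.3** blinds patients only.
- **Section 8.3** requires eligibility to be confirmed with the UNC coordinator before treatment starts. It does not tie release of the assignment to that step.
- **Section 1.3** reports that some physicians in the department already spare the parotids off trial, while others prefer standard fields.
- **Section 4.3.1** describes a second route, "with the observation arm (Consent form 2, arm C) offered to those who refuse randomization". For that arm, section 4.3.7 says: "WBRT will be delivered using standard or parotid sparing fields, per treating physician preference".
- **Section 4.3.1** also says that the screening questionnaires of patients who consent "will be assigned patient information (de-anonymized) and serve as their baseline quality of life data". For the others: "Questionnaires completed by patients who are found to be ineligible or who decline to enroll on the study will be destroyed".

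**The concern.** Random allocation protects against selection bias only if the person deciding whether to approach or enroll a patient cannot know which arm comes next. A list held at the site before enrollment removes that protection unless access is controlled, and no control is described.

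This trial is more exposed than most. Treating staff are not blinded, opposed preferences are on record (for the lead department; other sites are not described), and Arm C offers a legitimate exit with physician-chosen fields. Patients identified after radiotherapy has started also go to Arm C, and section 4.1 expects many of them, so a late approach would look routine.

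What matters is whether avoidance depends on risk. If it reflects field preference alone, accrual slows but the risk mix of the arms does not shift. If it depends on perceived risk of dry mouth, the primary comparison is biased, in either direction. Possible cues are available: the screening score, and the medications that section 4.3.10 treats as potential confounders. The documents give no figure for how well these predict an increase of 15 points or more.

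Detection afterwards would be partial. Patients who move to Arm C keep a baseline and follow the same assessments. Patients who decline both options have their questionnaires destroyed, and patients never approached leave no described trace.

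**Working it through.** **1. Do the described steps conceal the sequence?**

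- Randomizing after consent orders the steps. It does not hide the sequence from someone who can read it while deciding whom to approach.
- Patient blinding does not concern recruiting or treating staff.
- Central eligibility confirmation is due before treatment starts, which may be after the assignment has been seen.
- Knowing the arm before planning requires one assignment after consent. It does not require the list before enrollment.

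**2. The plan's own figure.** Inputs from section 7.2: 42% against 14%, one-sided 0.05, 80% power, chi-square test. With the pooled rate (0.42 + 0.14)/2 = 0.28:

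n = [1.645·√(2·0.28·0.72) + 0.842·√(0.42·0.58 + 0.14·0.86)]² / 0.28² = 30.7, so 31 per arm, as stated (power 80.3% by the normal approximation).

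Exact enumeration of the same test (31 per arm, reject if z ≥ 1.645) gives type I error 4.8% at 42/42 and power 81.8% at 42/14. This is the reference below.

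**3. Illustration of risk-related diversion.** The following are assumptions, not figures from the documents. Half of patients are high risk and half low risk, at 57%/27% or 62%/22% (each averages 42%). A share d of the high-risk half is steered away from one arm's slots.

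- Event rate in that arm = [0.5(1−d)·high + 0.5·low] / [0.5(1−d) + 0.5]
- Patients diverted per 45 filled slots (45 per arm, section 1.1) = 45/(1 − 0.5d) − 45

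For example, d = 20% with 57/27: (0.4·0.57 + 0.5·0.27)/0.9 = 40.3%, a spurious difference of 1.7 points; diverted = 45/0.9 − 45 = 5.

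Ranges cover the two sets of strata. Power for Arm A diversion holds Arm B at 14%.

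| d | Diverted per 45 | Spurious difference (points) | From Arm B slots: type I error | From Arm A slots: type I error | From Arm A slots: power |
|---|---|---|---|---|---|
| 0 | 0 | 0 | 4.8% | 4.8% | 81.8% |
| 10% | 2.4 | 0.8-1.1 | 5.4-5.7% | 4.0-4.2% | 79.5-80.1% |
| 20% | 5.0 | 1.7-2.2 | 6.2-6.8% | 3.2-3.6% | 76.8-78.1% |
| 40% | 11.3 | 3.8-5.0 | 8.5-10.2% | 1.9-2.4% | 69.4-72.9% |

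Diversion unrelated to risk leaves the rates at 42/42 and 42/14, so nothing changes. Equal diversion from both arms leaves type I error at 4.7-4.8%. Power is then 76-81% if Arm B keeps one third of the Arm A rate (a further assumption).

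**4. Room for adjustment.** Expected events at the planned rates are 31·0.42 + 31·0.14 = 17.4, which supports a very small binary model. The mean-change analysis in section 7.1 gives more room. Neither can adjust for unmeasured clinical judgement.

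**5. Why block size matters even without a list.** Treating staff know past assignments. With a fixed, known block size within a site (none is stated; 2, 4 or 6 assumed), 50%, 33% or 25% of assignments are certain in advance.

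**The case against.** The strongest reply is that the text is silent rather than openly wrong. It gives the list to the site, not to recruiters. It places randomization after consent, it involves a central coordinator, and it gives a practical reason for urgent cases. That is fair as a limit on the claim: the text permits foreknowledge and does not show it. It is not an answer, because a rule that sends the list out before enrollment and restricts nobody's access is followed perfectly well with an open list.

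Second, the false-positive scenario is the less natural one. A physician worried about dry mouth would sooner keep a high-risk patient out of Arm A, which makes the test conservative and costs power. Opposed preferences acting equally on both arms would leave type I error unchanged. Both points stand. Concern about marginal failure, also recorded in section 1.3, could still push patients away from Arm B, so inflation is not excluded.

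Third, strata, diversion rates and direction are all assumed, block size is unknown, and the number of patients still to be randomized is not stated. This also stands, and is why the size is given as unknown. Finally, out-of-hours logistics at several sites are not trivial; the envelope route is there for that reason.

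**Conclusion.** The concern holds and should be fixed. The textual gap is established with high confidence: sites get the sequence before enrollment, and no section conceals it. Bias is not demonstrated and its size is unknown.

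Under the assumed strata, the effect is small at 10% diversion. A type I error near 10% needs the wider strata, 40% diversion and the Arm B direction together. Diversion from Arm A slots costs up to about 12 points of power (81.8% to 69.4%). The case for change does not rest on these figures. It rests on the fact that selection on unmeasured judgement cannot be repaired in the analysis, while concealment prevents it cheaply.

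**What to change.** Replace the sentence in section 4.3.2 about giving each site a list with text such as:

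> The sequence is held at UNC and concealed from recruiting and treating staff. Block sizes vary at random and are not disclosed to sites. After signed consent and confirmed eligibility, and before treatment planning, one assignment is released per patient through the UNC coordinator or a web module. Out of hours, once consent and the eligibility checklist are signed, a person outside recruitment and treatment opens the next sequentially numbered, sealed, opaque envelope; eligibility is then confirmed with the coordinator before treatment start, as section 8.3 requires.

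Issue a new concealed sequence for the remaining patients at any site that held an open list, and state in the report who had access to the lists.

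Useful additions, secondary to the change above:

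- Compare baseline variables across Arms A, B and C. Split Arm C into patients who refused randomization and patients identified after radiotherapy began, whose baseline may be up to 5 days into treatment.
- Add a sensitivity analysis of the primary endpoint adjusted for baseline score.
- Optionally, keep a de-identified count of patients identified before radiotherapy (approached or not, consented, refused, Arm C), with a screening score only where a questionnaire was completed and the IRB agrees.

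**Cost.** One amendment, a new sequence and an added step in urgent cases. In hours, eligibility confirmation moves ahead of planning; out of hours, the envelope route keeps the section 8.3 timing but needs an independent person on hand. The Arm C comparison uses data already collected plus route of entry. Section 7.2 shows that enrollment has begun, so patients already randomized cannot be protected retrospectively.

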#### **4.3.3 Blinding**

This will be a single-blind study, where all enrolled patients are blinded to the type of WBRT fields used in their treatment in order to minimize reporting bias between the study arms.

[figure not shown]
#### **4.3.4 CT simulation**

Patients on all study arms will routinely undergo a CT scan for treatment planning.

Immobilization is achieved with an aquaplast mask form fitted on the patient's face and locked on to the table. Prior to the CT scan, a "scout X-ray" is taken to ensure the patient is in an acceptable position. A CT scan is then obtained through the treatment area, and including the entire neck. These images are used to create the radiation treatment plan. The planning CT scan is then transferred to the treatment planning software program. 3D conformal radiation plans will then be created for each patient.

#### **4.3.5 Treatment Planning and Delivery – Arm A: Standard WBRT (Control Arm)**

Patients randomized to the control arm will receive standard WBRT without delineation or avoidance of the parotid glands, as per typical practice (see Figure 4, below). Patients must be enrolled prior to treatment. Laterally arranged beams will be designed based on digitally reconstructed skull radiographs. A 5-10 mm margin is used around the cribriform plate and skull base, with inferior extension of the field to cover the entirety of the C1 and/or C2 vertebra, with at least a 2mm margin anterior to the vertebral bodies. The parotids will *not* be delineated for avoidance, and delineation of other organs at risk or the brain is optional, consistent with most national studies utilizing WBRT (see section 1.2.3). All treatment plans are monitored for quality assurance at departmental meetings in which radiation fields are presented for peer review. Weekly X-ray films are taken to verify the accuracy of patient set up on actual treatment days. The initial treatment will not proceed without physician verification of accurate patient set up.

**Figure 4. Control arm (Standard WBRT).** Example of a laterally arranged treatment field for standard WBRT used in the control arm, where a small margin is provided around the inferior skull border. The C1 vertebra is covered with a small anterior margin. No organs at risk are standardly delineated, though providers may opt to delineate the lens and orbits for avoidance, or the brain to ensure coverage.

[figure not shown]
#### **4.3.6 Treatment Planning and Delivery – Arm B: Parotid sparing WBRT (Intervention Arm)**

Patients randomized to the intervention arm will receive parotid sparing WBRT (see Figure 5, below). Patients must be enrolled prior to treatment.

[figure not shown]
- The left parotid will be delineated and named **Parotid\_Lt**
- The right parotid will be delineated and named **Parotid\_Rt**
- The **Parotid\_Lt** and **Parotid\_Rt** structures will be combined and named **Parotids\_Bilateral** for use in planning and dosimetric analysis.
- The **brain** will be delineated to the level of the foramen magnum, marked by the superior dens (see Figure 6, below), to ensure adequate target coverage.
- Laterally arranged beams will be designed based on both digitally reconstructed skull radiographs and CT anatomy. Radiation fields will be altered to minimize overlap with the **Parotids\_Bilateral** contour, while maintaining around a 1cm margin around the brain contour. All treatment plans are monitored for quality assurance at departmental meetings in which radiation fields are presented for peer review. Weekly X-ray films are taken to verify the accuracy of patient set up on actual treatment days.

Based on the results of the replanning analysis from LCCC 1540, 87% of patients were able to achieve a bilateral parotid V20Gy <25% while maintaining a 1cm margin around the brain, and the range of replanned bilateral parotid V20Gy was 1-35%. Thus, there will be a **goal to limit the Parotids Bilateral V20Gy to <25%, and lower if possible**. The following table summarizes the dose constraints of the parotid-sparing arm:

Parotid-sparing WBRT arm dose constraints (for Parotids Bilateral)	
Goal	V20Gy < 25%
Minor deviation	V20Gy $\geq$ 25% to < 35%
Major deviation	V20Gy $\geq$ 35%

**Figure 5. Intervention arm (Parotid sparing WBRT).** Example of a laterally arranged treatment field for parotid sparing WBRT used in the intervention arm. Cervical vertebrae are no longer considered in treatment planning. The parotids and brain must be delineated. Ensuring a 1 cm margin around the brain contour, the treatment field is altered to minimize overlap with the parotid glands.

**Figure 6. Intervention arm (Parotid sparing WBRT).** Contouring of the parotids (green, blue) and brain (red). The brain contour extends inferiorly to the most superior point of the dens of the C2 vertebra (dotted circle).

#### 4.3.7 Treatment Planning and Delivery – Arm C: Observational arm (WBRT protocol not specified)

Patients who decline randomization but consent to the observational arm will receive WBRT without the use of the above treatment planning guidelines. WBRT will be delivered using standard or parotid sparing fields, per treating physician preference. Patients may also enroll on this arm after initiation of WBRT, as long as the baseline questionnaire is completed within 5 days of initiation of treatment. These patients will complete the protocol-specified study assessments at the same time points as randomized patients.

#### 4.3.8 Treatment Planning and Delivery – Quality Assurance

Given that whole brain radiation is often delivered in situations of medical urgency, there will be no requirement for the PI or primary site to approve treatment plans before initiation of radiation. However, to ensure delivery of radiation as intended, *a digitally reconstructed radiograph containing the treatment field and any delineated organs at risk or targets will be sent to the study coordinator for the first four randomized patients at each non-primary site participating in the protocol.* If the treatment plans are not found to be adequate, the Principal Investigator will hold a meeting with the pertinent sites to discuss requested corrections for future patients. Patients who received the incorrect treatment (per randomization) will not be analyzed as part of the primary endpoint.

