### **2.4 Endpoints**

Primary endpoint: The primary endpoint will be the proportion of patients experiencing clinically significant xerostomia (defined as a  $\geq 15$  point increase in composite University of Michigan Xerostomia Questionnaire score [2]) *in randomized patients* from baseline to 1 month post-treatment.

Secondary endpoint #1: Freedom from marginal relapse, including CNS relapse in the inferior brain (defined as within 1 cm of the block edge overlying the blocked parotids), and the rate of upper cervical spine relapse (defined as relapses in the C1 or C2 vertebrae).

Secondary endpoint #2: Xerostomia (defined as a  $\geq 15$  point increase) at 1 month based on the use of standard vs. parotid sparing fields *in all patients, including randomized and non-randomized patients*.

Exploratory endpoint: [REDACTED]

[REDACTED]

Exploratory endpoint #2: [REDACTED]

[REDACTED].

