### **7.3 Data Analysis Plans**

The primary data analysis plan is to compare the proportion of patients in each randomization arm experiencing a  $\geq 15$  point xerostomia score increase between baseline and 1 month, with the use of a two group chi-square test. As sample size allows, linear mixed effects models will be explored to evaluate changes over time including all repeated measurements. It is anticipated that a significant number of enrolled patients will be unable to complete the 3 month (estimated 40% response rate) and 6 month (estimated 20% response rate) post-radiation questionnaires due to disease morbidity and mortality, so modeling may be limited to the earlier time points. In such a

scenario with significant patient dropout, separate analyses will be performed for patients with vs. without long term follow up.

Descriptive statistics will be provided for all scores at all time-points and to summarize the patient population. Secondary data analyses will estimate the time to marginal relapse (defined as within 1 cm of the block edge overlying the blocked parotids) and the time to upper cervical spine relapse (defined as relapses in the C1 or C2 vertebrae) in each randomization arm using the Kaplan Meier method. A log rank test will be used to compare these time to event outcomes. Furthermore, the above analyses exploring xerostomia will also be conducted in all patients (including those who refused randomization but consented for the observational arm).

A linear regression model will be used to further explore the dosimetric relationship between parotid dose and xerostomia, to supplement data from LCCC 1540.

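### Section 4.3.8 drops wrongly treated randomized patients from the primary endpoint; section 7.3 does not carry the rule, and no as-randomized analysis of that endpoint is kept

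*Combined protocol and SAP*

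**What the plan says.** Section 4.3.8 ends its account of plan review with the rule: "Patients who received the incorrect treatment (per randomization) will not be analyzed as part of the primary endpoint".

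Elsewhere the primary comparison is by assignment:

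- Section 2.1 sets the primary objective in randomized patients.
- Section 2.4: "The primary endpoint will be the proportion of patients experiencing clinically significant xerostomia", again in randomized patients.
- Section 4.3 gives the main purpose as to "compare the proportion of patients experiencing significant xerostomia in patients randomized to parotid sparing vs. standard WBRT".
- Section 7.3 plans to "compare the proportion of patients in each randomization arm experiencing a" rise of at least 15 points, using a chi-square test. It names no analysis set and does not refer to 4.3.8.

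The two techniques are described. Arm A receives "standard WBRT without delineation or avoidance of the parotid glands" (4.3.5). For Arm B, "Radiation fields will be altered to minimize overlap with the" combined parotid contour (4.3.6). V20Gy results in Arm B are graded as goal, minor deviation or major deviation, and no grade is called incorrect treatment.

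The data needed to classify patients are collected. Section 4.3.5 says "All treatment plans are monitored for quality assurance at departmental meetings in which radiation fields are presented for peer review", and 4.3.6 says the same. Parotid dosimetry is obtained in both randomized arms (4.3.10), and deviations are recorded (8.4.3). No section ties these data to the exclusion.

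Secondary endpoint #2 looks at xerostomia "at 1 month based on the use of standard vs. parotid sparing fields", in randomized and non-randomized patients together.

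**The concern.** Randomization makes the arms comparable as assigned. Removing patients because of the fields they later received breaks that comparability unless those removed have, on average, the same risk as those who stay. Nothing in the plan ensures this.

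The documents also leave the primary analysis open. An analyst working from 7.3 alone would keep a patient given the other arm's fields, in the assigned arm. An analyst who had also read 4.3.8 would drop that patient. Both would be following the protocol, and their primary results could differ.

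The phrase in 4.3.8 most naturally means treatment with the other arm's technique. However, the rule does not refer to 4.3.5 or 4.3.6, nobody is named to apply it, and it is not said to be applied without knowledge of xerostomia scores. Only patients are blinded (4.3.3).

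No other planned analysis of the primary endpoint restores the assigned groups. Secondary endpoint #2 groups by fields used, so it is an as-treated analysis.

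**Working it through.** **Inputs.** From 7.2: 42% v 14%, 31 per arm, one-sided 0.05, chi-square test, 70% completion, 90 enrolled. The number of wrongly treated patients and their risk are not in the documents; every value used for them below is an assumption.

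**1. The plan's own figure.** With mean proportion 0.28,

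n = [1.645·√(2 × 0.28 × 0.72) + 0.842·√(0.42 × 0.58 + 0.14 × 0.86)]² / 0.28² = 30.7, so 31 per arm. This reproduces.

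62 / 0.70 = 88.6, so 89 against the 90 planned. 90 × 0.70 = 63, one more than the 62 needed, so enrolment makes no real allowance for 4.3.8 exclusions.

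**2. Type I error under exclusion.** The null is 42% in both arms. Reject when (x_A/n_A − x_B/n_B) / √[p(1 − p)(1/n_A + 1/n_B)] ≥ 1.645, where p is the pooled proportion. Sum the binomial probabilities of all rejecting outcomes.

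If k patients with risk q are removed from an arm whose overall risk is 42%, the rest have risk (31 × 0.42 − kq) / (31 − k). For k = 4 and q = 0.60 this is (13.02 − 2.40) / 27 = 39.3%.

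| Excluded | Assumed risk of excluded | Risk of those left | Type I error |
|---|---|---|---|
| None | – | 42% | 4.8% |
| 2 from Arm B | 42% | 42% | 5.0% |
| 2 from Arm B | 60% | 40.8% | 6.2% |
| 4 from Arm B | 42% | 42% | 4.9% |
| 4 from Arm B | 60% | 39.3% | 7.4% |
| 4 from Arm B | 80% (extreme) | 36.4% | 11.3% |
| 4 from Arm B | 20% | 45.3% | 2.8% |
| 4 from Arm A | 80% | 36.4% | 1.9% |
| 4 from each arm | 80% | 36.4% in both | 5.5% |

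Exclusions at average risk leave the error near 5%. Inflation needs exclusions that are both one-sided and at high risk. Exclusions with the opposite pattern make the test conservative.

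**3. Power, as randomized v excluded.** Assume that crossover patients take the risk of the fields they received. With four Arm B crossovers the expected Arm B rate is (27 × 0.14 + 4 × 0.42) / 31 = 17.6%, and the difference is 42 − 17.6 = 24.4 points. With four in each arm, Arm A becomes (27 × 0.42 + 4 × 0.14) / 31 = 38.4%, and the difference is 20.8 points.

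| Crossovers | Difference as randomized | Exact power as randomized | Exact power if excluded at average risk |
|---|---|---|---|
| None | 28.0 points | 82% | 82% |
| 1 in Arm B | 27.1 | 79% | 81% |
| 4 in Arm B | 24.4 | 69% | 79% |
| 2 in each arm | 24.4 | 71% | 80% |
| 4 in each arm | 20.8 | 59% | 77% |

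**The case against.** The strongest reply is that the rule is narrow and its harm hypothetical. It covers only the primary endpoint. The log-rank comparisons by randomization arm, the descriptive statistics and the exploratory mixed models in 7.3 are not restricted by it. The reference to randomization, read with 4.3.5 and 4.3.6, gives a workable criterion. Fields are fixed in the plan record before any 1-month score exists, patients are blinded, and plans go to peer review. No crossover is documented. The primary set already loses about 27 of 90 patients to missing surveys (90 × 0.30), so an as-randomized analysis of those with surveys does not restore full protection either. It would also cost power if crossover is common.

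Most of this stands, and it limits the point in four ways:

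- A reader might infer that the plan keeps no as-randomized analysis of any kind. It does, for other outcomes; the gap is in the primary endpoint. The mixed models are conditional on sample size and do not replace the 1-month comparison of proportions.
- A reader might infer that no criterion exists. One can be built from the arm descriptions. What is missing is the link to them and a statement that classification ignores the scores.
- A reader might infer that a major V20Gy deviation leads to exclusion. The documents do not say so.
- A reader might infer from section 1.3 that crossover is likely. That section describes physicians' preferences off trial, not departures from assignment after consent.

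The reply does not explain why the stated comparison by randomized arm should drop randomized patients. Early fixing of the fields prevents outcome-driven choice of fields. It does not make the excluded patients typical, and it does not prevent a late classification by someone who has seen the scores.

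**Conclusion.** The point holds for the primary endpoint and should be fixed. Section 4.3.8 sets a post-randomization exclusion that 7.3 omits and that does not fit 2.1, 2.4, 4.3 and 7.3. No as-randomized result for the primary endpoint remains.

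It would go too far to call this a breach of intention-to-treat, because the documents never promise that analysis. It would also go too far to say that the result will be biased. Under assumed exclusions of two or four patients from one arm, type I error ranges from 1.9% to 11.3%. It stays near 5% if those excluded have average risk, and is 5.5% if four at 80% risk leave each arm. If wrong-arm treatment is rare, the practical effect is small. The sample size of 31 per arm is not in question.

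**What to change.** In 4.3.8, replace the sentence with:

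> Patients who received the other arm's technique stay in the primary analysis in the arm to which they were randomized (section 7.3).

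In 7.3, add:

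> The primary analysis includes all randomized patients with baseline and 1-month surveys, in the arm to which they were randomized, regardless of the technique delivered. A sensitivity analysis excludes patients not treated with their assigned technique: Arm A patients whose fields were altered to avoid the parotids, Arm B patients whose fields were not altered to avoid the parotids (whether or not these were delineated), and patients in either arm treated with a technique of neither arm. A V20Gy deviation alone does not count. Status is taken from the treatment plan for every randomized patient in both arms, without reference to xerostomia scores, by existing study staff. The number excluded in each arm is reported.

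Reconcile this with section 3.2, which allows subjects to be excluded or withdrawn, for example for intensity-modulated treatment.

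**Cost.** Wording, and one look at the plan for up to 90 patients; no added visits or enrolment. The real downside is the dilution shown in the power table. State it as a limitation and do not enrol more patients for it. The roughly 30% expected to lack a 1-month survey remain a separate problem, so the change removes one source of post-randomization selection, not all of it.
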